### **5.3 All-Treat (AT) Population**

The all-treat (AT) population will consist of the subset of ITT patients who took at least one dose of study treatment on this study. Patients will be analyzed based on the actual treatment received. This population will be used for primary analyses of safety.

### **5.4 The Proof of Concept Population**

The Proof of Concept (PoC) Population consists of all patients who are randomized in the study with confirmed SARS-CoV2 infection under protocol version 1.0 to 5.0. This is a proof-of-concept cohort and thus will be analyzed separately. Efficacy and safety endpoints will be presented for descriptive purpose. Patients will be analyzed in the treatment arm to which they were treated.

### **5.5 Application of Analysis Population**

Unless otherwise noted, the analysis populations that will be used for summaries of each set of data points are provided in Table 5.

**Table 5: Application of Populations for Summary**

	ITT Population	EE Population	AT Population	PoC Population
Disposition	X			X
Baseline Characteristics				
Demographics	X	X	X	X
Medical history	X		X	X
Disease history	X		X	X
Prior/concomitant medication	X	X	X	X
Tobacco use	X	X	X	X
Drug exposure and compliance			X	X
Efficacy Endpoints				
Primary efficacy endpoint	X	X		X
Key secondary efficacy endpoints	X	X		X
Other secondary endpoints	X			X
Safety Endpoints				
TEAEs			X	X
Labs			X	X
Vital signs			X	X
ECG			X	X

CCI

## 6. PATIENT SUMMARY

### 6.1 Patients Disposition

Patients' disposition will be tabulated by treatment arm and overall using ITT and PoC Population for the following categories:

- Number of randomized patients:
  - Number of patients received at least one dose of study treatment
  - Number of patients still on-treatment
  - Number of patients with treatment discontinuation
  - Primary reasons for treatment discontinuation

A by-patient listing of study completion information, including the reason for study withdrawal will be provided.

### 6.2 Demographic and Baseline Characteristics

The demographic and baseline data will be summarized by treatment arm and overall including:

- Age at screening (years)
- Age in categories
- Sex
- Race.
- Ethnicity
- Weight at baseline (kg)
- BMI at baseline (kg/m^2)
- Baseline use of concomitant therapies
- Baseline comorbidities
- Baseline comorbidities by medical history
- Smoking History
- Baseline cytokines (LDH, CRP, Ferritin)

Race will be collected wherever allowed and reported for the patients for whom it is known.

### 6.3 Medical/Surgical History

Medical history will be coded using the latest Medical Dictionary for Regulatory Activities (MedDRA) Version available. Summaries will be presented by System Organ Class (SOC) and Preferred Term (PT) with numbers and percentages by treatment arm. Each patient will be counted only once in each SOC or SOC/PT summary.

In the summary table, medical history will be sorted by alphabetic order SOC and then by decreasing frequency PT within each SOC. In cases of SOC's or PT's with equal frequencies, medical history will be sorted alphabetically.

#### **6.4 Disease History**

Patients' disease history will be summarized by treatment arm including following variables:

- Days from first COVID-19 symptoms to randomization date, calculated as (date of randomization - date of initial onset of COVID-19 symptoms + 1)
- Days from admission to hospital to randomization date, calculated as (date of randomization - date of admission to hospital + 1)
- Days from date of confirmed COVID-19 diagnosis to randomization date, calculated as (date of randomization - date of confirmed COVID-19 diagnosis + 1)

#### **6.5 Prior and Concomitant Medications**

All medications will be coded using the latest WHO Drug Dictionary version available.

Prior medications are defined as those medications started prior to the administration of study treatment. Concomitant medications are defined as those medications taken after first dose of study treatment. Hence medications started before receiving study treatment but continuing after will be considered as both prior and concomitant medications.

Prior and concomitant medications will be summarized with numbers and percentages by ATC level 2 (therapeutic level), ATC level 4 (generic level) and standardized medication name separately. A patient who takes more than one medication will be counted only once if these medications belong to the same extended ATC classification. The summary tables will be sorted by alphabetic order ATC levels and standard medication names.

#### **6.6 Protocol Deviations**

Protocol deviations will be recorded by the site staff separately from the clinical database. They may also be identified through programmable checks of the data.

A by-patient listing for all major protocol deviations will be provided.

#### **6.7 Extent of Study Treatment Exposure and Compliance**

##### **6.7.1 Extent of Study Treatment Exposure**

The extent of exposure for the study treatment will be assessed by treatment arm using the following variables:

- Duration (weeks) of exposure defined as (date of last study treatment - date of first study treatment + 1)
- Duration of exposure in category (<=1 week, (1, 2] weeks, (2, 3] weeks, (3, 4] weeks)
- Total dose received (mg) defined as sum of doses received
- Average dose received (mg/week) defined as total dose received/duration of exposure
- Number and percentage of patients with dose reduced w/wo dose delayed
- Number and percentage of patients with dose delayed w/wo dose reduced
- Number and percentage of patients with concurrent dose reduced and delayed
- Number and percentage of patients with dose held
- Number and percentage of patients with missed dose

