**Study Treatment/Treatment Groups, Dose, and Mode of Administration:**

A dose of 20 mg selinexor or matching placebo will be administered orally on Days 1, 3, and 5 of each week for up to 2 weeks. If the patient is tolerating therapy and clinically benefitting, as defined below, dosing can continue for an additional 2 weeks (on Days 15, 17, 19, 22, 24, and 26).

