**SCHEDULE OF ASSESSMENTS**

**Table 1: Schedule of Assessments for admitted patients only**

| Activity/Assessment                            | Screening  | Dosing Period                     |           |           |           |            |            |             |             |            |            | End-of-Treatment | Hospital Discharge | Safety Follow-Up / End of Study  |
|--|------------|-----------------------------------|-----------|-----------|-----------|------------|------------|-------------|-------------|------------|------------|------------------|--------------------|--|
|  | D -2 to D1 | D1 ±1 day                         | D3 ±1 day | D5 ±1 day | D8 ±1 day | D10 ±1 day | D12 ±1 day | D 15 ±1 day | D 19 ±1 day | D22 ±1 day | D26 ±1 day | D14/28*          |                    |  |
| Informed Consent b                  | X          |                                   |           |           |           |            |            |             |             |            |            |                  |                    |  |
| Inclusion/Exclusion                            | X          |                                   |           |           |           |            |            |             |             |            |            |                  |                    |  |
| Demographics                                   | X          |                                   |           |           |           |            |            |             |             |            |            |                  |                    |  |
| Medical history                                | X          |                                   |           |           |           |            |            |             |             |            |            |                  |                    |  |
| Disease History                                | X          |                                   |           |           |           |            |            |             |             |            |            |                  |                    |  |
| Vital signs c                       | X          | Twice daily during Hospital Stay  |           |           |           |            |            |             |             |            |            |                  |                    |  |

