**Table 4: Selinexor Dose Modification Steps for Adverse Reactions**

| Recommended Starting Dosage                                     | First Reduction  |
|---|--|
| 20 mg
Days 1, 3 and 5 of each week
(60 mg total per week) | 20 mg
Days 1 and 3 weekly
(40 mg total per week) |

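### SAP 6.7.1 gives exposure duration in days but labels it weeks, and dividing by 7 still leaves too short a denominator for the average weekly dose

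*SAP*

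**What the plan says.** SAP 6.7.1 (Extent of Study Treatment Exposure) lists four linked variables. The first is the length of treatment: "Duration (weeks) of exposure defined as (date of last study treatment - date of first study treatment + 1". The second groups that length into four bands, each one week wide, with the last band ending at 4 weeks. The third is a plain sum of the milligrams taken. The fourth is a rate built from the first and third: "Average dose received (mg/week) defined as total dose received/duration of exposure". No division by 7 appears in that section or elsewhere in the SAP.

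The protocol synopsis has 20 mg given on Days 1, 3 and 5 of each week, with a limit of two weeks unless the patient qualifies for an extension. For those who qualify, "dosing can continue for an additional 2 weeks (on Days 15, 17, 19, 22, 24, and 26". The Schedule of Assessments (Table 1) places the second-week doses on Days 8, 10 and 12. Protocol Table 4 gives the starting regimen as "60 mg total per week" and the reduced one (Days 1 and 3 only) as 40 mg per week.

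**The concern.** There are two separate defects.

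**Unit.** A date difference plus 1 is in days. The label, the categories and the mg/week denominator all treat it as weeks, so the tabulated average would be mg per day under a mg/week label.

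**Denominator.** Suppose the unit is put right. The period from first to last dose contains every dose but only one day of the interval that follows the last one. On a Day 1, 3, 5 schedule that makes the period one or two days too short for a weekly rate, which matters when treatment lasts only one to four weeks.

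At stake is whether the exposure table can be read against the planned regimen. An average that runs high can hide lost doses. The size of the excess also depends on when patients stop, so different discontinuation patterns would distort a comparison of average dose between arms.

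**Working it through.** **Inputs.** 20 mg per dose. Dosing days 1, 3, 5, 8, 10, 12 (2-week course), continuing on 15, 17, 19, 22, 24, 26 (4-week course). Planned weekly dose 60 mg, which reproduces as 3 × 20.

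**Formulas.** D = last dose day − first dose day + 1. As written, average = total mg / D. With the unit corrected, average = total mg / (D/7).

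**Patients dosed exactly to plan, by day of last dose:**

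| Last dose day | Total mg | D | As written | After dividing D by 7 |
|---|---|---|---|---|
| 1 | 20 | 1 | 20.0 | 140.0 |
| 3 | 40 | 3 | 13.3 | 93.3 |
| 5 | 60 | 5 | 12.0 | 84.0 |
| 8 | 80 | 8 | 10.0 | 70.0 |
| 10 | 100 | 10 | 10.0 | 70.0 |
| 12 | 120 | 12 | 10.0 | 70.0 |
| 15 | 140 | 15 | 9.3 | 65.3 |
| 17 | 160 | 17 | 9.4 | 65.9 |
| 19 | 180 | 19 | 9.5 | 66.3 |
| 22 | 200 | 22 | 9.1 | 63.6 |
| 24 | 220 | 24 | 9.2 | 64.2 |
| 26 | 240 | 26 | 9.2 | 64.6 |

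**As written.** The 2-week completer is (60 − 10.0)/60 = 83% below plan and the 4-week completer (60 − 9.23)/60 = 85% below. A last dose on Day 3 falls in the category for more than 2 and up to 3 weeks. A last dose on Day 5 or later fits no category.

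**After dividing by 7.** Every on-schedule stopping day falls in the right category. The average is still high: 70.0/60 is +16.7% for a 2-week completer and 64.6/60 is +7.7% for a 4-week completer.

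**Lost doses, after dividing by 7:**

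- Five of six doses, last on Day 12: 100/(12/7) = 58.3. Over the two dosing weeks it is 100/2 = 50.
- Reduced schedule for 2 weeks (four doses, last on Day 10): 80/(10/7) = 56.0, against 40 planned.
- Reduced schedule for 4 weeks (eight doses, last on Day 24): 160/(24/7) = 46.7, against 40 planned.

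**Counting full dosing weeks.** 60/1, 120/2 and 240/4 all return 60.

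**The case against.** The unit slip is close to self-correcting: the categories end at 4 weeks, so a programmer who obtained 12 or 26 would probably add the division. First-to-last-dose plus 1 is also an accepted convention for duration. Nothing in the documents says the average must equal 60 mg/week, since Table 4 states a regimen and not a check on this statistic. Total dose, reductions, delays, holds and missed doses are reported separately, and SAP 6.7.2 adds compliance.

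Much of this stands. The duration convention is usable once divided by 7, and the 10.0 and 9.2 figures may never be printed. The average is a different matter. It is a rate per week, the planned regimen is its natural comparator, and a patient dosed to plan should not show 70. Compliance does not fill the gap, because SAP 6.7.2 removes from the scheduled doses those missed through interruption or for other reasons outside the patient's choice.

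A reader might infer more than the documents support:

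- *That the average is wrong for every patient even with the unit fixed.* Six doses with the last on Day 14 give 120/(14/7) = 60, though only by coincidence of the delay.
- *That the error always grows as treatment shortens, so early stoppers always look more intensely dosed than completers.* The figure is 70.0 for last doses on Days 8, 10 and 12 alike, and a Day 22 stopper (63.6) shows less than a Day 26 completer (64.6).
- *That readings of safety by dose are compromised.* SAP section 8 plans safety summaries by treatment arm and none by dose or dose intensity.

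**Conclusion.** The point holds in two parts. The formula as written returns days under a weeks label, giving 12 and 26 'weeks' and 10.0 and 9.2 'mg/week' for on-plan 2- and 4-week courses against the planned 60. With the unit corrected, duration and its categories are sound, but the average weekly dose still reads 70.0, 64.6, 84 and 140 for on-plan courses of 2 weeks, 4 weeks, 1 week and a single dose. A missed dose or a reduced schedule can look close to full dosing.

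These figures assume doses on the nominal protocol days; the ±1-day windows shift them slightly (six doses with the last on Day 13 give 64.6 instead of 70.0).

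The reach is limited. Efficacy analyses, total dose, compliance, the planned safety analyses and the stopping criteria in Protocol 9.5 do not use the formula. This is a correction to descriptive exposure tables, worth making because it is cheap and the printed result would contradict the protocol's own weekly dose.

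**What to change.** 1. Define duration in weeks as (last dose date − first dose date + 1)/7 and keep the existing categories.
2. Give average dose its own denominator, by one of two routes:
   - **Dosing weeks.** Divide total mg by the number of 7-day dosing weeks, counted from the first dose, through the end of the week containing the last dose. This gives 120/2 = 60 and 240/4 = 60 for completers, 100/2 = 50 for five of six doses, and 80/2 = 40 for two weeks on the reduced schedule. It reads low for stops within a week (20/1 = 20 after one dose, 80/2 = 40 after a Day 8 stop), so the table needs a footnote.
   - **Relative dose.** Report total mg received divided by total mg planned through the last dose date, keeping interrupted and held doses in the denominator. On-plan patients show 100% whenever they stop; five of six doses with the last on Day 12 shows 100/120 = 83.3%. State whether planned means the starting regimen after a reduction.

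Ending the denominator on the day before the next scheduled dose is not a clean alternative. It gives 20/(2/7) = 70 after a Day 1 stop, 40/(4/7) = 70 after a Day 3 stop and 80/(9/7) = 62.2 after a Day 8 stop, and no dose is scheduled after Day 26.

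The cost is a few lines of SAP text and a small change to the exposure program. The calculation needs only dose dates and amounts, so no new data are required.

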### 6.7.2 Treatment Compliance

Treatment compliance (%) will be summarized by treatment arm, calculated as

$$\frac{\text{total number of doses taken}}{\text{Total number of doses scheduled}} \times 100.$$

Note that the number of scheduled doses does not include doses missed due to treatment interruption or other reasons not related to patient choice.

The number and percentage of patients with study treatment compliance  $\geq 70\%$  will be provided.

## 7. EFFICACY ANALYSES

Efficacy analyses will be primarily performed in ITT population. For primary and key secondary endpoints, efficacy analyses using the EE population will be considered as supportive for the corresponding analyses in the ITT population. Efficacy analyses in PoC population will be descriptive in nature.

Please refer to Table 6 below for efficacy endpoints and the corresponding definitions.

**Table 6: Efficacy Endpoints and Definitions**

Endpoint	Definition
Primary Endpoint	
Day 14 Ordinal Scale improvement (OSI2-14)	Proportion of patients with at least a 2 points improvement (increase) in the Ordinal Scale by Day 14. Baseline score is defined as the last score measured before first dosing. The improvement is assessed between the baseline score and the latest score on or before Day 14, End of study (EoS) date, or database cut date, whichever occurs first.
Key Secondary Endpoints	
Time to an improvement of 2 points using Ordinal Scale (TTCI-2)	The time from randomization to an improvement of 2 points on the Ordinal Scale. For patients who didn't achieve clinical improvement of 2 points, 
 
If no death event by Day 28, they will be censored on the last contact date, on or before Day 28, EoS date, or database cut date, whichever occurs first.
 
 If they died by Day 28, they will be censored on Day 28.
Overall death rate on Day 28 (DR-28)	Proportion of patients died on or before Day 28.
Rate of mechanical ventilation (RMV)	Proportion of patients who ever used invasive mechanical ventilation or ECMO during the hospital stay.
Time to mechanical ventilation (TTMV)	Time to the first use of mechanical ventilation. For patients who never used mechanical ventilator, the censoring date is defined as the death date or last contact date (if no death), on or before EoS or database cut date, whichever occurs first.

Additional Secondary Endpoints	
Time to recovery (TTR)	Time to improvement from baseline score of 3 to $\geq 4$ or from a baseline score of 4 to $\geq 5$ by Day 28. For patients who didn't achieve recovery, the censoring rule will be the same as that in TTCI-2.
Day 7 Ordinal Scale 2 points improvement (OSI2-7)	Proportion of patients with at least a 2 points improvement (increase) in the Ordinal Scale from baseline to Day 7. The improvement is assessed between the baseline score and the latest score on or before Day 7, End of study (EoS) date, or database cut date, whichever occurs first.
Day 7 Ordinal Scale 1 point improvement (OSI1-7)	Proportion of patients with at least a 1 point improvement (increase) in the Ordinal Scale from baseline to Day 7. The improvement is assessed the same as in OSI2-7.
Day 14 Ordinal Scale 1 point improvement (OSI1-14)	Proportion of patients with at least a 1 point improvement (increase) in the Ordinal Scale from baseline to Day 14. The improvement is assessed the same as in OSI2-14.
Time to an improvement of 1 point on the Ordinal Score (TTCI-1)	The time from randomization to an improvement of 1 point on the Ordinal Scale. For patients who didn't achieve clinical improvement of 1 point, the censoring rule will be the same as that in TTCI-2.
Overall survival (OS)	Time since randomization to death date, or the last contact date with patient status being alive, on or before EoS or database cut date, whichever occurs first.
Overall death rate on Day 14 (DR-14)	Proportion of patients died on or before Day 14.
Rate of ICU admission	Proportion of patients with ICU admission.
Length of hospitalization	Length of hospital stay defined as cumulative length of hospital stay.
Length of ICU stay	Cumulative length of ICU stay.
Duration of mechanical ventilation	Cumulative number of days with invasive mechanical ventilation or ECMO

PaO 2 :FiO 2 and/or oxygenation index over time	PaO 2 :FiO 2 and/or oxygenation index over time. Will be summarized by visit using descriptive statistics.
---	--

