## 7.2 Analyses of Secondary Efficacy Endpoints

### 7.2.1 Analyses of Key Secondary Efficacy Endpoints

If the primary endpoint, OSI2-14, is significant in ITT population, the following key secondary endpoints in ITT population will be sequentially tested in the order listed below. If any null hypothesis is not rejected in this sequence of tests, formal sequential testing will be stopped and the analyses of any endpoints thereafter will be nominal only.

- Time to clinical improvement (TTCI-2)
- Overall Death rate on Day 28 (DR-28)
- Rate of mechanical ventilation (RMV)
- Time to mechanical ventilation (TTMV)

For binary endpoints (DR-28, RMV), the difference in rates between treatment arms will be calculated with a 95% confidence interval (CI). Comparison between 2 treatment arms will be performed using the Cochran-Mantel-Haenszel (CMH) test stratified by the randomization stratification factors. The CMH estimate of the odds ratio and its 95% CI and the p-value for testing the treatment difference will be reported.

For time to event endpoints (TTCI-2, TTMV), the number and percentage of patients with the corresponding events will be reported. Median event times with 95% CIs will be estimated by Kaplan-Meier (KM) method for each treatment arm. KM curves by treatment arms will be provided.

The following analysis stratified on randomization strata will be performed:

- Log-rank test stratified to compare the event times between treatment arms

- Hazard ratios of treatment effect with 95% CI estimated by Cox proportional hazards model with Efron's method of tie handling

Non-stratified log rank test and Cox proportional hazards model will be performed as sensitivity analyses.

The Kolmogorov-type Supremum test will be conducted to assess the validity of the proportion hazards assumption in all fitted Cox proportional hazards models. If there is evidence for a violation of the proportional hazards assumption, interaction terms between time-dependent terms and treatment variable (selinexor vs. placebo) will be added to assess time-varying treatment effects.

In sensitivity analysis for RMV, analyses will be conducted with patients who ever used one of the respiratory assistances as below:

- Non-invasive positive pressure mechanical ventilation (CPAP/BiPAP)
- High-flow nasal cannula
- Invasive mechanical ventilation
- Extracorporeal membrane oxygenation (ECMO)

For TICI-2, sensitivity analyses will be performed in the same manner as OSI2-14.

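### Deaths without ventilation count as non-events for RMV and are censored for TTMV, so the reported ventilation results can favour the arm with more such deaths

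*SAP*

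**What the plan says.** SAP Table 6 defines RMV as "Proportion of patients who ever used invasive mechanical ventilation or ECMO during the hospital stay". Death is not part of the event, so a patient who dies unventilated stays in the denominator as a non-event.

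For TTMV, a patient who was never ventilated is censored at death, or at last contact if alive: "the censoring date is defined as the death date or last contact date (if no death"). The comparison in SAP 7.2.1 is "Log-rank test stratified to compare the event times between treatment arms", with a Cox model.

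The same table handles death differently for TTCI-2: "If they died by Day 28, they will be censored on Day 28". Those patients remain at risk, without the event, to the end of the window. Time to recovery and TTCI-1 inherit that rule.

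SAP 7.2.1 tests TTCI-2, DR-28, RMV and TTMV in that order once the primary endpoint is significant. "If any null hypothesis is not rejected in this sequence of tests, formal sequential testing will be stopped", and later analyses become nominal. Protocol 9.4.1 also lists RMV as key secondary and puts the death rate before it. TTMV is key secondary only in the SAP.

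No planned analysis in the visible text adds death to either ventilation endpoint:
- The RMV sensitivity analysis widens the types of respiratory support.
- TTMV gets unstratified tests and a proportional-hazards check.
- The efficacy evaluable population drops deaths within 24 hours of randomization, which moves further from counting early deaths.

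**The concern.** Death prevents later ventilation. Scoring it as a non-event gives it the same value as recovery. Censoring it treats the patient as someone who could still be ventilated and who resembles those remaining at risk. In severe COVID-19 that is doubtful, because respiratory deterioration leads to both outcomes.

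The distortion can run either way. If more selinexor patients die before or without intubation, RMV falls on selinexor and looks like benefit. If selinexor prevents such deaths and some of those patients are then ventilated, RMV rises and a real benefit is hidden. What is at stake is the reading of two of the SAP's four key secondary endpoints. Separate mortality rates do not let a reader correct RMV, because they do not show which deaths were unventilated.

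**Working it through.** **Inputs from the documents.** The planned ITT size is 247 (Protocol synopsis). At 1:1 that is 124 vs 123. SAP 7.1.1 says about the first 50 were randomized 2:1, which gives roughly 33 + 99 = 132 vs 17 + 98 = 115. The significance level is not in the visible text; two-sided 0.05 is assumed from the 95% confidence intervals. The documents give no figure for RMV or TTMV to reproduce.

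**Assumed, because the documents give no rates.** Ventilation-or-death, c, is equal in both arms at 20%, 25% or 30%. Unventilated deaths, d, are 10% vs 5%, or 12% vs 4% (selinexor vs placebo).

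**Step 1: RMV as written.** In each arm RMV = c − d. For c = 20% and d = 10% vs 5%, RMV is 10% vs 15%, although bad outcomes are equal.

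**Step 2: chance that RMV is nominally significant for selinexor.** The check is an unstratified two-proportion z test, simpler than the planned stratified CMH test. With p₁ and p₀ the two RMV values and p̄ the pooled rate:

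probability = Φ[(−1.96·s₀ − (p₁ − p₀)) / s₁], where s₀ = √{p̄(1−p̄)(1/124 + 1/123)} and s₁ = √{p₁(1−p₁)/124 + p₀(1−p₀)/123}.

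For 10% vs 15%, s₀ = 0.0421 and s₁ = 0.0420, so (−0.0825 + 0.05)/0.0420 = −0.77, and Φ = 22%.

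| c, both arms | Unventilated deaths | RMV | Odds ratio | Formula | Simulation (200,000 trials) |
|---|---|---|---|---|---|
| 20% | 10% vs 5% | 10% vs 15% | 0.63 | 22% | 22% |
| 25% | 10% vs 5% | 15% vs 20% | 0.71 | 18% | 18% |
| 30% | 10% vs 5% | 20% vs 25% | 0.75 | 15% | 16% |
| 20% | 12% vs 4% | 8% vs 16% | 0.46 | 49% | 50% |
| 25% | 12% vs 4% | 13% vs 21% | 0.56 | 39% | 39% |
| 30% | 12% vs 4% | 18% vs 26% | 0.62 | 33% | 33% |

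The composite gives about 2.5%, the chance level. Using 132 vs 115 moves the results by at most about 1 point. Swapping the arms gives almost the same probabilities in favour of placebo.

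**Step 3: TTMV (2,000 simulated trials, unstratified log-rank).** Assume 25% of each arm deteriorates to the point of needing ventilation on Days 1-14, and 30% of ventilated patients die. On selinexor, 40% of those who deteriorate die unventilated; on placebo, none do. Then RMV is 25% × 0.6 = 15% vs 25%. Deaths are 10% + 0.3 × 15% = 14.5% vs 0.3 × 25% = 7.5%. RMV is nominally significant for selinexor in 51% of trials and TTMV in 43%. The composite gives 2.3%, binary or time-to-event. With unventilated deaths in 40% vs 10% of those who deteriorate, the figures are 33% for RMV and 28% for TTMV.

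**Step 4: boundary case.** Let the extra deaths be independent of the need for ventilation, at 15% vs 5%. TTMV stays at chance (2.4%), and RMV hardly moves (24.1% vs 24.6%; 3.0% significant). At 30% vs 5%, TTMV is 2.2% and RMV 5.0%.

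**Step 5: the gate.** In the Step 2 scenarios, assume 30-50% of ventilated patients die. DR-28 and RMV are then both significant for selinexor in 0.1-0.4% of trials (10% vs 5%) and 0.04-0.25% (12% vs 4%). This is before requiring OSI2-14 and TTCI-2 as well. If a DR-28 rejection for harm also opened the gate, that would add 0.2-1.7% and 1-11% respectively. In the more extreme Step 3 scenario, DR-28 significant in either direction together with RMV favouring selinexor occurs in 16% of trials.

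**The case against.** The strongest reply is the test order. A reader might take 15-22% against 2.5% as inflated type I error for a key secondary claim. The documents do not support that: RMV and TTMV are formally tested only after OSI2-14, TTCI-2 and DR-28 are all rejected, and Step 5 shows how rarely DR-28 and RMV would both favour selinexor. This stands, and it confines the problem mainly to nominal estimates, odds ratios, hazard ratios and Kaplan-Meier curves. It is not a complete answer, because SAP 7.2.1 does not say which direction of DR-28 rejection opens the gate. It also does nothing for the opposite bias. A gate opened by harm would, however, come with significantly higher mortality on selinexor.

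Second, excess deaths would be visible. Day 14 and Day 28 death rates, overall survival and causes of death are all reported, and Protocol 9.5 has halting criteria for death and for invasive ventilation. The ordinal scale already ranks death (1) below ventilation (2). This stands, but none of it shows deaths without ventilation by arm.

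Third, censoring at death is a recognised way to estimate the cause-specific hazard. A reader might infer that TTMV is biased whenever mortality differs. Step 4 shows otherwise: the deaths must be linked to the need for ventilation. That link is plausible here, but it is a condition.

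Fourth, all rates are assumed, and holding the composite exactly equal is a constructed case. That is correct; the figures show what could happen, not what is expected.

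**Conclusion.** The point holds for the reported RMV results, and conditionally for TTMV. Table 6 scores an unventilated death as a non-event for one and censors it for the other, unlike TTCI-2, and nothing planned adds death to either. Under the assumed rates, RMV nominally favours selinexor in about 15-22% of trials (33-50% in the wider scenario) when ventilation-or-death is the same in both arms. TTMV moves the same way only when deaths remove patients who would have been ventilated.

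A formal false claim with DR-28 also favouring selinexor is very unlikely, at about 0.04-0.4% of trials. The weakness lies in interpreting nominal results and in the unstated direction of the DR-28 gate. It merits a change to the SAP but does not threaten the primary analysis. Whether the composite replaces RMV and TTMV or stands beside them is partly a choice of estimand.

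**What to change.** In SAP Table 6 and 7.2.1:

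- Add invasive ventilation, ECMO or death by Day 28 as a planned analysis alongside RMV and TTMV, both as a binary endpoint and as time from randomization to the first of these. Alternatively, make it their main definition, keep ventilation alone as supportive, and align the protocol's key secondary endpoint.
- Report the cumulative incidence of ventilation with death as a competing event.
- Tabulate deaths without ventilation by arm.
- State that DR-28 must be rejected in favour of selinexor before RMV and TTMV are formally tested.

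Ventilation and death are already collected, so the cost is SAP wording and one or two extra tables. The composite is less specific to ventilation and overlaps with DR-28. Making it the main definition also requires the protocol change; adding it as a planned analysis does not redefine the protocol endpoint.
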